### **3.2 Primary outcome variable**

The change from Baseline in weekly Itch Severity Score (ISS7) at Week 12 will be used as the primary efficacy variable.

The UPDD will be completed twice daily (morning and evening; CSP Table 3) to capture key measures of urticaria disease activity including the ISS. Compliance with twice-daily completion of the UPDD will be reviewed at every visit (CSP Table 2).

Participants will be asked to document twice a day (morning and evening) the intensity of itch they experienced over the previous 12 hours. The criteria used to define itch severity score (ISS) on a 0- to 3-point scale are shown in Table 2.

**Table 2 Assessment of CSU itch activity in study participants**

Score	Itch severity
0	None
1	Mild
2	Moderate
3	Severe

Scoring criteria are as defined in omalizumab Study Q4882g (EUDRACT: 2010-022785-27).

The mean of the morning and evening itch scores for each day is taken as the ISS for the day. For daily ISS, if either the morning or evening score is missing, the non-missing score for that day (morning or evening) is used as the daily score. If both morning and evening scores are missing, the daily score is not calculated. The ISS7 is the sum of ISS for the previous 7 days.

If a participant has at least 4 non-missing ISS scores, the ISS7 is defined as the sum of the available daily ISS scores divided by the number of days with non-missing ISS scores, multiplied by 7. If there are less than 4 non-missing daily ISS scores then the weekly ISS7 is missing for that week.

For each visit, the 7 daily scores prior to that visit will be used for calculating the weekly scores, thus the day of the visit will not be included into the weekly score.

The minimum ISS7 is 0 and the maximum is 21. The baseline ISS7 will be the sum of the ISS during the 7 days prior to day of randomisation. The ISS7 at Week 12 will be the sum of the daily ISS during the previous 7 days.

For the primary estimand, all available scheduled visit data up to Week 24 will be included regardless of intercurrent events like randomised treatment adherence, rescue medication received, or early discontinuation. The primary analysis will follow a treatment policy approach with missing at random assumption.

Participants will complete all PRO assessments using a handheld device. The handheld device will be the only accepted source of PRO data. In case of technical issues with the device, a web-based emulator of the device will be available.

### **3.3 Secondary outcome variables**

#### **3.3.1 Urticaria Activity Score (UAS7)**

UAS7 is part of the UPDD which will be completed twice daily as described above (Section 3.2).

Participants will be asked to document twice a day (morning and evening) the number of hives they experienced over the previous 12 hours on a 0- to 3-point scale as shown in Table 3.

The mean of the morning and evening hive scores for each day is taken as the hives severity score (HSS) for the day. The sum of the HSS and the ISS (see Section 3.2) for the day is the urticaria activity score (UAS) for the day.

**Table 3 Assessment of CSU hives activity in study participants**

Score	Intensity (number) of hives
0	None
1	Mild (1 – 6 hives/12 hour)
2	Moderate (7 – 12 hives/12 hour)
3	Intense (> 12 hives/12 hour)

Scoring criteria are as defined in omalizumab Study Q4882g (EUDRACT: 2010-022785-27).

HSS7 is the sum of HSS for the previous 7 days. UAS7 is the sum of UAS for the previous 7 days, ie, the sum of ISS7 and HSS7.

Scoring for HSS/HSS7 and UAS/UAS7 with respect to calculations and missing data will be as described for ISS/ISS7 above.

The minimum UAS7 is 0 and the maximum is 42. The baseline UAS7 will be the sum of the UAS during the 7 days prior to day of randomisation. The UAS7 at Week 12 will be the sum of the daily UAS during the previous 7 days.

The key secondary endpoint variable is change from baseline of UAS7 score at Week 12. The primary analysis of the key secondary endpoint will use the same treatment policy strategy estimand as outlined for the primary endpoint.

The change from baseline in UAS7 at Week 24 will be analysed as secondary endpoint.

The change from baseline in UAS7 at Week 52 will be analysed after the extension period.

#### **3.3.2 Proportion of responders of UAS7**

The UAS7 is defined for the key secondary endpoint variable above (Section 3.3.1).

The proportion of responders with  $UAS7 \leq 6$  at Week 12 and Week 24 will be analysed. The proportion of participants with complete  $UAS7$  response ( $UAS7 = 0$ ) at Week 12 and Week 24 will be analysed.

The proportion of responders with  $UAS7 \leq 6$  at Week 52 and the proportion of participants with complete  $UAS7$  response ( $UAS7 = 0$ ) at Week 52 will be analysed after the extension period.

In the statistical analyses, a binary variable will take on value 1 if a participant is defined as a responder, and value 0 for non-responder, and will be used as the response variable for the efficacy analysis.

If  $UAS7$  response is missing at a respective analysis visit (e.g. Visit 12 or 24) then the participant will be treated as a non-responder at that visit. Participants with a missing baseline  $UAS7$  response will have missing responder status.

### **3.3.3 Hives severity score (HSS7)**

$HSS7$  is defined for the key secondary endpoint variable above (Section 3.3.1).

The minimum  $HSS7$  is 0 and the maximum is 21. The baseline  $HSS7$  will be the sum of the  $HSS$  during the 7 days prior to day of randomisation. The  $HSS7$  at Weeks 12 and 24 will be the sum of the daily  $HSS$  during the previous 7 days.

The change from baseline in  $HSS7$  will be analysed at Weeks 12 and 24.

The change from baseline in  $HSS7$  score at Week 52 will be analysed after the extension period.

### **3.3.4 Itch Severity Score (ISS7)**

$ISS7$  is defined for the primary endpoint variable above (Section 3.2).

The change from baseline in  $ISS7$  will be analysed at Week 24 as secondary endpoint.

The change from baseline in  $ISS7$  at Week 52 will be analysed after the extension period.

### **3.3.5 Time to $\geq 5$ point decrease in ISS7**

$ISS7$  is defined for the primary endpoint variable above (Section 3.2). The time to  $\geq 5$  point decrease (clinically relevant decrease) in  $ISS7$  will be summarised.

This will be defined as change from baseline of the first  $\geq 5$  point decrease in  $ISS7$ . Time from randomisation to the first clinically relevant decrease is derived as follows:

*(Date of first  $\geq 5$  point decrease – Date of randomisation + 1).*

The time to  $\geq 5$  point decrease for participants who do not experience a  $\geq 5$  point decrease during the treatment period will be censored at EOT visit for participants who complete the study. Participants who withdraw from the study or are lost to follow-up before EOT visit will be censored at the last visit date at which a decrease in ISS7 could be assessed.

The time to  $\geq 5$  point decrease in ISS7 will be analysed over the double blind period up to Week 24, and also over the whole study period up to Week 52 after the extension period.

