4.1.2 Investigational Product Dosing Regimen

Participants who meet entry criteria will be randomised 3:3:3:3:4 by the interactive voice/web response system (Interactive Voice Response System [IVRS]/Interactive Web Response System [IWRs]) to one of the 5 treatment sequences described in Section [4.1](#).

[Figure 3](#) presents an overview of the IP that will be administered for each randomised treatment group.

Figure 3 Investigational Product Administration

^a In the extension period, participants will receive benralizumab on a Q8W or Q4W dosing regimen, as predetermined at randomisation (Visit 2). Participants randomised to receive benralizumab Q8W in the extension period will also receive placebo at intervening study visits when they are not receiving benralizumab.

Q4W, every 4 weeks; Q8W, every 8 weeks.

Dosing Regimen at Visits 2, 3, and 4 (Initial Double-blind 12-week Treatment Period)

All participants will receive randomised double-blind study medication Q4W at Visits 2, 3 and 4 (ie, Weeks 0, 4, and 8; [Figure 3](#)).

Dosing Regimen at Visits 5, 6, and 7

Participants randomised to receive either 60 mg or 30 mg benralizumab during the initial 12-week period will receive 30 mg benralizumab Q4W at Visits 5, 6 and 7 (ie, Weeks 12, 16 and 20; [Figure 3](#)).

Participants receiving placebo will continue to receive placebo ([Figure 3](#)).

Dosing Regimen at Visits 8 Through 14

At Week 24 (Visit 8), participants initially randomised to benralizumab 60 mg or benralizumab 30 mg will receive benralizumab 30 mg Q4W or Q8W according to their original randomisation at Week 2. Participants randomised to the Q8W regimen will receive placebo at Week 24 and benralizumab 30 mg at Week 28 ([Figure 3](#)).

At Weeks 24, 28, and 32 (ie, Visits 8, 9 and 10), participants initially randomised to placebo will receive benralizumab 30 mg Q4W. At Week 36 (ie, Visit 11), participants randomised initially to placebo will receive benralizumab 30 mg Q8W; these participants will receive placebo at Week 36 and benralizumab 30 mg at Week 40 (Visit 12) ([Figure 3](#)).

Participants transitioned to the benralizumab 30 mg Q8W dosing regimen will remain on the Q8W dosing regimen. Participants will continue to receive SC injections Q4W at the study site visits; thus, participants receiving benralizumab 30 mg Q8W will receive placebo at every other site visit ([Figure 3](#)).

The final dose of benralizumab or placebo will be administered at Week 48 (Visit 14).

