4.4 End of Study Definition

The end of study is defined as the last expected visit/contact of the last participant participating in the study.

A participant is considered to have completed the study when he/she has completed his/her last scheduled visit/telephone contact.

See [Appendix A 6](#) for guidelines for the dissemination of study results.

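### Time to a 5-point ISS7 decrease: event-free completers are censored at the EOT visit rather than at their last evaluable ISS7, which can pull the Kaplan-Meier response curve down

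*SAP*

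**What the plan says.** SAP 3.3.5 sets two censoring rules for participants who never show the decrease.

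- Completers: their time "will be censored at EOT visit for participants who complete the study".
- Others: "Participants who withdraw from the study or are lost to follow-up before EOT visit will be censored at the last visit date", specifically the last one where a change in ISS7 was assessable.

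The same section applies these rules to two analyses: the endpoint "will be analysed over the double blind period up to Week 24, and also over the whole study period up to Week 52". It gives no separate censoring date for the Week 24 analysis.

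Four other provisions matter.

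- Protocol 4.4: "A participant is considered to have completed the study when he/she has completed his/her last scheduled visit/telephone contact". No ISS7 is needed to count as a completer.
- Protocol 7.1.1.1 lets participants who stop IP replace site visits with monthly telephone contact.
- SAP 3.2: "If there are less than 4 non-missing daily ISS scores then the weekly ISS7 is missing for that week". Protocol 8.1 accepts PRO data only from the handheld device (SAP 3.2 adds a web emulator as back-up), so symptoms reported by telephone cannot become an ISS7.
- SAP 4.2.7.5 presents Kaplan-Meier quartiles and plots by treatment group, with no test and no hazard ratio. SAP 4.1.1 leaves this endpoint outside the multiplicity procedure.

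**The concern.** Kaplan-Meier estimation requires that everyone in the risk set could be seen to have the event. The rule for withdrawn and lost participants respects this, but the rule for completers does not, because it follows the visit calendar and not the data. A completer whose ISS7 ends early is carried forward as a known non-responder. Each such person enlarges the denominator at later visits and adds nothing to the numerator, so the estimated response can only fall relative to censoring at the last ISS7.

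The error could differ between arms if diary lapses or IP discontinuation differ. That matters because Protocol 4.3 makes time of onset one basis for judging the induction dose.

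The completer rule also does not fit the Week 24 analysis. Under SAP section 4 the primary lock is targeted for when all participants have completed 24 weeks. Many event-free participants will then still be in the extension: they have not completed, withdrawn or been lost, and they have no EOT visit.

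**Working it through.** **Figures in the plan.** The documents give no event rate, missing-ISS7 rate or power for this endpoint. The only design figure, 90% power, concerns the primary endpoint. It reproduces: 54 versus 36 after 10% dropout, difference 4.7, SD 6 and two-sided 2.5% give 91.9% (normal) or 91.1% (noncentral t). It does not bear on this point, so every rate below is an assumption.

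**Set-up.** Visits are every 4 weeks, six of them up to Week 24. Let *c* be the true response by Week 24, with constant hazard per visit, so the share event-free after *k* visits is (1 − c)^(k/6). A share *f* of the arm has no ISS7 after Week 12 (three visits) but counts as completing. Unassessed people are assumed to respond at the same rate as the others.

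**Censoring at the last ISS7.** The Week 24 estimate is *c*.

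**Censoring at EOT.** The unassessed stay at risk, with their event-free share fixed at its Week 12 value, (1 − c)^(1/2):

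estimate = 1 − [(1 − f)(1 − c) + f(1 − c)^(1/2)]

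shortfall = f × [(1 − c)^(1/2) − (1 − c)]

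Example with c = 50%, f = 10%: 0.10 × (0.707 − 0.500) = 0.021, so 47.9% is reported instead of 50%.

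Week 24 estimate under the rule as written (shortfall in points):

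| True c | f = 5% | f = 10% | f = 20% |
|---|---|---|---|
| 30% | 29.3 (0.7) | 28.6 (1.4) | 27.3 (2.7) |
| 50% | 49.0 (1.0) | 47.9 (2.1) | 45.9 (4.1) |
| 70% | 68.8 (1.2) | 67.5 (2.5) | 65.0 (5.0) |

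If ISS7 stops after Week 4, the term (1 − c)^(1/2) becomes (1 − c)^(1/6). The shortfall then runs from 1.2 points (c = 30%, f = 5%) to 10.4 points (c = 70%, f = 20%). This is the most extreme case tried.

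**Only terminal gaps count.** If ISS7 is missing at some visits and later resumes, both rules keep the person at risk throughout. They differ only when no evaluable ISS7 follows.

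**Which visit is EOT?** Protocol 6.3.2 labels Visit 16 as EOT. Protocol Table 2 puts Visit 15 at Week 52 and Visit 16 at Week 60, while Protocol 7.1 calls Week 60 Visit 17. Protocol 7.1 also writes of the IPD/EOT visit as one visit. These passages must be reconciled before EOT can serve as a censoring date.

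**The 52-week curve for the placebo sequence.** From Week 24, "participants initially randomised to placebo will receive benralizumab 30 mg Q4W", and time still runs from randomisation. Let *p* and *b* be the assumed 24-week response on placebo and on benralizumab. There are seven visits from Week 28 to Week 52, so the expected first decreases after the switch, of 40 participants, are 40 × (1 − p) × [1 − (1 − b)^(7/6)].

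- p = 70%, b = 50%: 40 × 0.30 × 0.555 = 6.7
- p = 30%, b = 80%: 40 × 0.70 × 0.847 = 23.7

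The curve up to Week 24 is unchanged. Of the placebo rates tried (30%, 50% and 70%), only 30% leaves the median unreached by Week 24. The median then falls at Week 32 to 36, on benralizumab.

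**The case against.** The strongest defence is that few people will meet the condition. ISS7 comes from a home diary, not from site visits. Only participants who withdraw from the study return the device (Protocol 7.2), and Protocol 7.1.1.1 does not say that the diary stops under telephone follow-up. If IPD and EOT are one visit for those who stop IP, they are censored about 4 weeks after the last dose and are not held to Week 52. The planned 10% dropout concerns people who would already be censored correctly, and the SAP expects little missing data. All of this stands. It limits the size, but does not justify the rule: a completer whose diary lapses is still mishandled, and the IPD/EOT reading is not settled.

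Three stronger readings are tempting, and the documents do not support them.

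- *The EOT rule credits placebo with benralizumab responses.* It applies only to people without a decrease, so it cannot create an event. Later decreases enter the placebo sequence's 52-week curve because nothing censors at the switch. That curve describes one of five randomised sequences (SAP 4.1), and Protocol 9.4.2.2 says the group is presented but not formally compared. The placebo-controlled comparison is the separate Week 24 analysis.
- *The Week 24 estimates are biased because EOT lies beyond Week 24.* For anyone assessed through Week 24, a later censoring date leaves the estimates up to Week 24 unchanged. This part is a missing specification.
- *This is the only evidence on onset.* Protocol 4.2 links the Week 12 primary assessment to onset, and SAP 4.2.6.1 reports treatment differences at every scheduled visit.

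**Conclusion.** The completer rule in SAP 3.3.5 is wrong as written: it ignores when ISS7 was last evaluable and is inconsistent with the rule beside it. It lowers estimated response relative to censoring at the last ISS7, in any arm with unassessable completers. With an assumed 10% of an arm lacking ISS7 after Week 12, the understatement at Week 24 is about 1.4 to 2.5 points; over 5% to 20% it is about 0.7 to 5 points. These figures assume that unassessed people respond like the others. If they would in fact not respond, the EOT rule does no harm.

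The Week 24 analysis also lacks a usable censoring date, and the 52-week placebo-sequence curve needs a clear label. The point is minor: the endpoint is secondary and descriptive, and no test or formal conclusion depends on it.

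**What to change.** In SAP 3.3.5, replace both censoring rules with one: every participant without a decrease is censored at the date of the last evaluable ISS7. For the double-blind analysis, cap this at the last ISS7 on or before the first extension dose, or at the Week 24 assessment for those who do not enter the extension. State which visit EOT means and reconcile Protocol 6.3.2, 7.1 and Table 2.

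In the 52-week output, label the placebo arm as a placebo-to-benralizumab sequence and mark the Week 24 switch on the plot. Optionally, show time from the first benralizumab dose as a separate curve, using the pre-switch baseline that SAP 3.1.1 already allows.

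The cost is about two sentences in the SAP, a plot label and, if wanted, one extra curve. No new data are needed.

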### 3.3.6 Measures of angioedema activity

The UPDD includes a daily yes/no question asking whether the participant experienced angioedema during the past 24 hours. If yes, the participant is asked a follow-up question about how they treated the swelling:

- 0 = Did nothing
- 1 = Took some prescription or non-prescription medication,
- 2 = Called my doctor, nurse or nurse practitioner,
- 3 = Went to see my doctor, nurse or nurse practitioner,
- 4 = Went to the emergency room at the hospital,
- 5 = Was hospitalized.

The percentage of angioedema free days will be calculated over the past 7 days.

$$(number\ of\ angioedema\ free\ days\ / number\ of\ non-missing\ responses) * 100$$

The number of non-missing responses for angioedema during the past 24 hours is the sum of days with response of yes or no, and excludes missing responses.

Summaries of the percentage of angioedema free days over the past 7 days will be produced. In addition, presence of angioedema in each 7 day period will be calculated where a participant will be considered to have had angioedema if they have at least one day with angioedema present in the 7 day period.

For the follow-up question, the frequency of each response over the past 7 days will be calculated for each participant.

For each visit, the 7 daily responses prior to that visit will be used for calculating the weekly proportion of angioedema free days over the past 7 days, and for the presence of angioedema in the past 7 days, thus the day of the visit will not be included into the weekly assessment. This approach is consistent with the derivations of the primary endpoint.

Measures of angioedema activity at Weeks 12 and 24 will be assessed in all participants and in the subgroups of participants with angioedema at baseline, and those with history angioedema.

Measures of angioedema activity at Week 52 will be assessed in all participants and in the subgroups of participants with angioedema at baseline, and those with history angioedema, after the extension period.

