#### **4.2.7.6 Measures of angioedema activity**

Measures of angioedema activity will be assessed in the overall population and repeated in participants with angioedema at baseline and in those with history angioedema.

Descriptive summaries of proportion of angioedema free days over the past 7 days, and proportion of patients with angioedema in the past 7 days, will be produced by treatment group and visit. A statistical model may also be used to analyse this data if appropriate (MMRM analyses, see Section [4.2.7.1](#)).

For the follow-up question, the frequency and percentages of each response over the past 7 days will be presented for number of participants and for number of responses per participant, presented by treatment group and visit.

The summaries will also be presented for durations of Week 4-12 and Week 4-24.

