#### 8.1.1 Missing data description

Tabular summaries for the percentage of participants by the reason for discontinuation of randomised treatment as well as for withdrawal from the study will be presented by treatment to describe why participants discontinue from randomised treatment or withdraw from the study. The time to discontinuation of randomised treatment and withdrawal from the study will be presented using Kaplan Meier plots (overall and split by treatment related/not treatment related reason for discontinuation, as defined in [Table 11](#)). Dependent on these outputs additional exploratory analyses may be produced as deemed necessary to further understand the pattern of missing data.

Descriptive summaries of number and percentage of participants using rescue medication and change of background medications will be provided by treatment group.

For primary endpoint variable ISS7 and key secondary endpoint variable UAS7, the summaries of number and percentage of participants with missing/non-missing daily assessments will be presented by treatment group and visit. This will summarise the amount of daily responses used in the calculation of the weekly scores.

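### The weekly angioedema measures have no minimum number of diary days: the percentage becomes imprecise, and the presence measure leans towards less angioedema where the diary is incomplete

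*SAP*

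**What the plan says.** SAP 3.3.6 derives two measures from the seven daily yes/no answers before each visit.

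- Percentage of angioedema-free days: free days divided by answered days. On the denominator the SAP says "The number of non-missing responses for angioedema during the past 24 hours is the sum of days with response of yes or no, and excludes" unanswered ones.
- Presence in the week: "a participant will be considered to have had angioedema if they have at least one day with angioedema present in the 7 day period".

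No number of answered days is required for either. Nothing says how to class a week with few answers or none.

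The itch score from the same diary is treated differently. SAP 3.2 computes it "If a participant has at least 4 non-missing ISS scores" and adds: "If there are less than 4 non-missing daily ISS scores then the weekly ISS7 is missing for that week". SAP 3.3.1 extends this to two further scores: "Scoring for HSS/HSS7 and UAS/UAS7 with respect to calculations and missing data will be as described for ISS/ISS7 above". Angioedema is not named there.

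The analysis is in SAP 4.2.7.6: "Descriptive summaries of proportion of angioedema free days over the past 7 days, and proportion of patients with angioedema in the past 7 days, will" appear by group and visit, with a model only if appropriate. SAP 4.1 makes the analysis set the denominator for categorical summaries unless another is stated, and 4.2.7.6 states no other. The completeness summary in SAP 8.1.1 covers two scores only: "For primary endpoint variable ISS7 and key secondary endpoint variable UAS7, the summaries of number and percentage of participants with missing/non-missing daily assessments will be" given by group and visit.

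**The concern.** A weekly score built from one or two answers is weak, and the SAP accepts this for the itch, hives and combined scores only down to four days. For angioedema there is no floor, and the two measures fail in different ways. The percentage becomes coarse. Presence becomes directional, because it can be positive only if a 'yes' was recorded, and an unanswered day can never supply one.

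This direction is the reverse of the one chosen for UAS7 response, where SAP 3.3.2 counts a missing score as non-response. Angioedema activity at Weeks 12 and 24 is a listed secondary endpoint. If diary completion differed between arms, the arm with the emptier diary would show a lower proportion with angioedema for that reason alone, and the planned completeness tables would not report on the angioedema item.

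**Working it through.** The documents give no figure for these measures, so there is nothing to reproduce. The check applies the two stated rules to a week with m answered days.

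**Percentage.** The formula is free days / m × 100.

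- m = 0: 0/0, undefined.
- m = 1: only 0 or 100.
- m = 2: 0, 50 or 100.
- m = 4: 0, 25, 50, 75 or 100.

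One 'yes' and six blanks gives 0/1 = 0%. Counting blanks as free would give 6/7 = 85.7%, so blanks are not counted as free here. If days are missing at random and a participant has angioedema on a fraction q of days, the expected percentage is 100(1 − q) for every m from 1 to 7. Taking days as independent, the SD is 100√(q(1 − q)/m). At an assumed q = 0.2 that is 40.0 at m = 1, 20.0 at m = 4 and 15.1 at m = 7. The loss is in precision.

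**Presence.** One 'no' plus six blanks contains no 'yes' and scores the same as seven 'no' answers. A week with no answers also contains no 'yes'. With independent days, missing at random, the chance of being scored present is 1 − (1 − q)^m:

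| Assumed q | m = 1 | m = 2 | m = 4 | m = 7 |
|---|---|---|---|---|
| 0.05 | 5.0% | 9.8% | 18.5% | 30.2% |
| 0.10 | 10.0% | 19.0% | 34.4% | 52.2% |
| 0.20 | 20.0% | 36.0% | 59.0% | 79.0% |
| 0.30 | 30.0% | 51.0% | 76.0% | 91.8% |

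**Clustering.** Protocol 8.3.6 describes episodes lasting hours or days, with resolution taking up to 72 hours, so independence is doubtful. Take a two-state Markov chain with an assumed day-to-day correlation of 0.5 and q = 0.2. A 'no' day is followed by another with probability 1 − 0.2 × 0.5 = 0.9. The chance of presence is then 1 − 0.8 × 0.9^6 = 57% with seven days, 1 − 0.8 × 0.9^3 = 42% with four consecutive days, and 20% with one. The gap between seven days and one falls from 59 points to 37.

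**Blank weeks.** Protocol 9.2 assumes 10% dropout. Read literally, a placebo group of 40 with 4 blank weeks keeps 40 as denominator while only 36 can score present. The displayed proportion is 36/40 = 0.9 times that among participants with answers.

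**The case against.** The SAP says of these derivations: "thus the day of the visit will not be included into the weekly assessment. This approach is consistent with the derivations of the primary endpoint". A reader might infer that the four-day minimum comes with that consistency. The sentence closes a statement about the seven-day window and the exclusion of the visit day, and when the SAP extends the missing-data rule, in 3.3.1, it says so. The inference is not secure enough to program from.

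A reader might also infer that missing days count as angioedema-free in both measures. For the percentage the text says the opposite, so that reading fails. Nor do the documents show that completion will differ between arms, or that any bias would favour benralizumab.

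There are real safeguards. Inclusion criterion 7 requires 6 of 7 daily assessments before randomisation, which largely protects baseline angioedema status. Protocol 8.1 has diary compliance checked at least weekly. The ISS7 and UAS7 completeness tables come from the same diary and would give a partial signal. It is only partial because a daily itch score survives on either a morning or an evening entry, while angioedema is a single daily question. Summaries over Weeks 4-12 and 4-24 draw on more days, though they carry no completeness rule either.

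The best objection concerns the remedy. A recorded 'yes' proves angioedema that week whatever the blanks hide, so a blanket four-day rule discards certain positives. That cost stands. But keeping short weeks only when they contain a 'yes' selects on the outcome. At q = 0.2 and three answered days, the 1 − 0.8^3 = 48.8% of weeks retained would all score present, against 79% for complete weeks. A rule that ignores the content of the answers is the more defensible choice.

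**Conclusion.** The point holds in a limited form. Neither weekly angioedema measure has a minimum number of answered days. For the percentage the consequence is imprecision, with an undefined value when nothing is answered. It is not a systematic tilt, provided days are missing independently of angioedema. For presence, unanswered days, and blank weeks under the default denominator, act as 'no angioedema', which biases the measure downwards where completion is poorer.

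The size in this trial is unknown. The 79%, 59% and 20% figures illustrate the mechanism under independent days, days missing at random and an assumed 20% daily rate. They should not be read as an estimate of bias, because the documents give no daily rate and no completion rate, and clustering narrows the gaps. The comparison between arms is distorted only to the extent that completion differs. The practical weight is minor: the measures are secondary, mainly descriptive and outside the multiplicity procedure.

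**What to change.** Make three changes to the SAP before unblinding at the primary database lock.

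1. In 3.3.6, set both weekly measures to missing unless at least 4 of the 7 daily answers are present, whatever those answers are.
2. In 4.2.7.6, use participants with an evaluable week as the denominator for presence.
3. In 8.1.1, add the angioedema item to the diary-completeness summary by group and visit.

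No new data are needed and the primary analysis is untouched. The cost is that some participant-weeks become missing, including some short weeks with a recorded 'yes'. The documents do not allow their number to be estimated. Under-ascertainment is reduced but not removed: at 4 to 6 answered days it remains, as the 59% against 79% illustration shows for four.
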